## 6 STUDY FLOW DIAGRAM

Abbreviations: CRS, chronic rhinosinusitis; CT, computed tomography; d, day; FSO, frontal sinus ostia/ostium; LM, Lund-Mackay; RSI, Rhinosinusitis Symptom Inventory; SBD, sinus balloon dilation; SNOT, Sino-Nasal Outcome Test.

## 7 SCHEDULE OF ASSESSMENTS

Assessments	Screening	Baseline/ Procedure (≤ 30 d from consent date)	Day 21 (± 7 d)	Day 45 (primary endpoint) (± 7 d)	Day 90 (± 14 d)	Day 180 (end of study) (± 14 d)
Informed consent	X					
Medical/surgical history	X					
CT scan 	X			X		X
Endoscopic evaluation & video recording	X 	X 	X	X	X	X
SNOT-22 questionnaire		X 				X
RSI questionnaire		X 				X
CRS side-specific symptom questionnaire		X 	X	X	X	X
In-office bilateral frontal SBD		X				
Randomization		X				
PROPEL Contour placement in FSO 		X				
Patient satisfaction questionnaire					X	X
Adverse event reporting	X	X	X	X	X	X
Device deficiency reporting		X	X	X	X	X
Concomitant medications	X	X	X	X	X	X

Abbreviations: CT, computed tomography; d, day; FSO, frontal sinus ostia/ostium; RSI, Rhinosinusitis Symptom Inventory; SBD, sinus balloon dilation; SNOT, Sino-Nasal Outcome Test.

 Screening CT must be performed ≤ 90 days prior to the baseline procedure to confirm the diagnosis of CRS. The follow-up CT at Day 45 and 180 shall be performed after endoscopic evaluation and debridement to ensure no implant remnants are present on the scan. All CTs should be uploaded for centralized blinded review.

 Screening endoscopic evaluation can be done at the baseline. Baseline values are entered into EDC.

 Complete endoscopic evaluation, SNOT-22, RSI and CRS side-specific symptom questionnaires prior to the baseline procedure. Assess implant apposition after the baseline procedure.

 Treatment side only.

## 8 BACKGROUND INFORMATION

### 8.1 Literature Review

Endoscopic sinus surgery (ESS) is recommended for patients with chronic rhinosinusitis (CRS) who have failed appropriate medical therapy (Orlandi 2021). While ESS has been demonstrated to be effective in reducing patient-reported symptoms in the short term, longer-term success rates have been reported in the range of 76% to 98% (Naidoo 2012, Ramadan 1999). Meanwhile, a relatively large number of patients continue to be symptomatic or experience recurrent symptoms or revision surgery within 1-2 years. Causes of surgical failure are numerous and include lateralization of the middle turbinate, adhesion formation between the middle turbinate and lateral nasal wall, ostial stenosis, persisting or recurrent mucosal edema, and polyposis. The same post-operative failure mechanisms within the ethmoid sinus apply to the frontal recess and frontal sinus ostia. These include formation of scarring, adhesions, synechiae, recurrent inflammation, and polyposis (Chandra 2004).

Many surgeons consider the postoperative treatment regimen to be as important as the surgery itself (Bugten 2006). There is strong evidence that postoperative endoscopic examination of the sinonasal cavity provides prognostic information concerning the potential for future episodes of sinusitis and that patients whose cavities became normal post-operatively are less likely to require revision (Kennedy 2000). Meticulous post-operative care following ESS involves several follow-up visits over the ensuing months. Maintenance of the surgical result is accomplished by routine endoscopic examination, meticulous cleaning of the cavity using saline rinses, debridement or other manipulations to remove adhesions, and adjustments in pharmacotherapy. Formation of adhesions, scarring, synechiae, middle turbinate lateralization, ostial stenosis and edema are major concerns often addressed by use of sinus stents and injectable gels. To address these post-operative issues, Intersect ENT (Menlo Park, CA) developed the PROPEL, PROPEL Mini and PROPEL Contour Sinus Implants.

The PROPEL Contour Sinus Implant was approved on 23 February 2017 for placement in maxillary and frontal sinuses following sinus surgery in CRS patients to maintain patency of the sinus ostia. Positive data from the PROPEL Contour Sinus Implant cohort of the PROGRESS study, a prospective, randomized, blinded, multi-center trial of 80 patients designed to assess the safety and efficacy of the implant when placed in the frontal sinuses following surgery (Luong 2018, Singh 2019), and a non-randomized, open-label EXCEED study in 15 patients for frontal and maxillary ostia, supported the approval. The study met its primary efficacy endpoint, demonstrating a statistically significant 65% relative reduction in the need for post-operative interventions, such as the need for additional surgical procedures or the need for oral steroid prescription, compared to surgery alone. The study utilized an intra-patient control design to assess the safety and efficacy of the PROPEL Contour Sinus Implant when placed following surgery performed in operating room on one sinus side compared to surgery alone on the contralateral side. The study results showed that placement of the PROPEL Contour Sinus Implant in the FSO

[figure not shown]
maintained sinus patency by reducing inflammation, scarring and polypoid edema. The study also confirmed that implant placement in the FSO poses negligible safety risks.

## **8.2 PROPEL Contour Sinus Implant**

### **8.2.1 Description**

A summary description of the PROPEL Contour Sinus Implant (**Figure 1**) is provided below. For more detailed delivery system and implant information, refer to the Instructions for Use (IFU). The PROPEL Contour Sinus Implant (part # 70033) is designed to accommodate the size and variability of the human sinus anatomy. The implant is intended to be inserted by a physician under endoscopic visualization and once positioned, is designed to be self-retaining against the mucosal surface in the area of the frontal recess/FSO.

The PROPEL Contour Sinus Implant is fabricated from a bioabsorbable monofilament polymer material commonly used in a variety of medical products, including dissolvable sutures. The implant is designed with an hour-glass shape to aid in anchoring / apposition to the tissue with the following dimensions: waist diameter = 15.5 mm (nominal), outer diameter = 27.0 mm (nominal), and height = 8.0 mm (nominal).

**Figure 1: PROPEL Contour Sinus Implant**

### **8.2.2 Intended Use**

The PROPEL Contour Sinus Implant is intended for use in patients  $\geq$  18 years of age to maintain patency of the frontal and maxillary sinus ostia following sinus surgery and locally deliver steroids to the sinus mucosa. The PROPEL Contour Sinus Implant separates/dilates mucosal tissues prevents obstruction by adhesions/scarring and reduces edema. The implant reduces the need for post-operative intervention such as surgical adhesion lysis and/or use of oral steroids.

## **9 STUDY OBJECTIVE AND ENDPOINTS**

The objective of the EXPAND study is to evaluate the efficacy of PROPEL Contour placement in the FSO following in-office bilateral frontal SBD in patients with CRS.

## 9.1 Primary Efficacy Endpoint

Side-to-side difference in FSO patency at Day 45 based on cross-sectional area of FSO using CT measurements performed by an independent, blinded reviewer.

## 9.2 Secondary Endpoints

- CT grading by an independent, blinded reviewer (Day 45, 180):
  - Cross-sectional area of FSO (Day 180 only)
  - FSO minimum diameter
  - FSOT volume
  - Zinreich's modified Lund-Mackay score for the frontal sinus
  - Lund-Mackay score for the frontal sinus
- CT grading by clinical investigators (Day 45, 180):
  - Lund-Mackay score for the frontal sinus
- Need for post-operative intervention as determined by clinical investigators based on endoscopic evaluation (Day 21, 45, 90, 180):
  - Repeat frontal SBD warranted or performed for restenosis/occlusion in the frontal recess/FSO; or
  - Surgical intervention warranted or performed to debride obstructive adhesions/scarring or for restenosis/occlusion in the frontal recess/FSO; or
  - Oral steroids warranted or prescribed to resolve recurrent edema in the frontal recess/FSO
- Endoscopic grading by clinical investigators (Day 21, 45, 90, 180):
  - Adhesion/scarring grade in the frontal recess/FSO and ethmoid sinus
  - Inflammation score in the frontal recess/FSO
  - Polypoid edema in the frontal recess/FSO
  - Polyp grade in the ethmoid sinus
- Patient-reported outcomes:
  - CRS side-specific symptom score (Day 21, 45, 90, 180)
  - SNOT-22 score (Day 180)
  - RSI score (Day 180)
- Implant delivery success rate by clinical investigators

### **9.3 Exploratory Endpoints**

- Patient satisfaction (Day 90, 180)
- Health-economic measures to determine health-care resource utilization (see Section 9.5)

### **9.4 Safety Measures**

All adverse events (AEs) for each subject from the time the subject gives informed consent through Day 180 will be recorded in the electronic data capture (EDC) system and monitored. Each AE will be evaluated by the clinical investigators for their seriousness and relationship to the study devices. Where possible and if applicable, AEs will be localized to a sinus location.

Safety will be determined by assessment of, adverse device effects (ADE), serious adverse events (SAEs), unanticipated adverse device effect (UADE) and unanticipated serious adverse device effect (USADE) from enrollment through Day 180 post-procedure (Section 4). All events will be separated between those attributed to PROPEL Contour Sinus Implant, those attributed to Cube Navigation System, VenSure™ Nav Balloon Device, Inflation device, Balloon Dilatation Procedure, Implant Placement Procedure, and those that are a mix or indistinguishable.

## 10 STUDY DESIGN

This is a post-market, randomized, intra-patient controlled, blinded, multicenter trial enrolling 80 randomized subjects from up to 20 US sites. No single site should enroll more than 16 subjects (20% of the total enrollment) for this study. Study subjects will be randomized following a successful in-office bilateral frontal BSD to receive one PROPEL Contour Sinus Implant on one FSO side (treatment), while the contralateral side serves as a control (see Section 6). Subjects are expected to return for 4 follow-up visits at Day 21, 45, 90 and 180 (end of study). Endoscopic evaluation will be conducted at each visit, and CT scan will be repeated at Day 45 and 180 (see Section 7).

## 11 STUDY POPULATION

Patients ( $\geq$  18 years of age) with confirmed diagnosis of CRS who are candidates for in-office frontal SBD because they present with bilateral stenosis of the FSO and in whom placement of the PROPEL Contour is feasible and medically appropriate as determined by clinical investigator.

### 11.1 Inclusion Criteria

Subjects are eligible for the study if they meet *all* the following criteria:

#### General inclusion criteria

- a. Patient has provided written informed consent using a form approved by the reviewing IRB.
- b. Patient is 18 years of age or older.
- c. Patient is willing and able to comply with protocol requirements.
- d. Patient has confirmed diagnosis of CRS per International Consensus Statement on Allergy and Rhinology: Rhinosinusitis 2021 (ICAR:RS) guidelines.

Patient must have  $\geq$  12 weeks of:

Two or more of the following symptoms:

- nasal obstruction or congestion
- nasal discharge (rhinorrhea or post-nasal drip)
- facial pain/pressure
- reduction/loss of smell

And one or more of the following findings:

- Evidence of inflammation on paranasal sinus examination or CT

- Evidence of purulence coming from paranasal sinuses or ostiomeatal complex
- e. In the opinion of the investigator, treatment with the PROPEL Contour Sinus Implant as an adjunct to frontal BSD with a 6 mm balloon is technically feasible and clinically indicated in both FSO.
- f. Female patients of reproductive age and potential must not be pregnant or nursing, and patient agrees to avoid becoming pregnant during their participation in the study.

*CT Imaging inclusion criteria*

- g. Patient has bilateral disease in the frontal sinus (Lund-Mackay score  $\geq 1$  on each side) on CT scan performed  $\leq 90$  days prior to the baseline procedure.

*Intraprocedural inclusion criteria*

- h. Patient is able to tolerate topical/local anesthesia.
- i. Confirmation of bilateral FSO access with navigation assistance
- j. A successfully completed in-office bilateral balloon dilation of the FSO with no complication on either side that, in the opinion of the investigator is amenable for PROPEL Contour Sinus Implant placement in both FSO.

## 11.2 Exclusion Criteria

Subjects are eligible for the study if they meet *none* of the following criteria:

*General exclusion criteria*

- a. Patient has structural obstruction that precludes endoscopic visualization of one or both FSOs prior to implant placement.
- b. Patient had prior Draf III surgery.
- c. Patient had prior sinus surgery or ESS  $\leq 30$  days from the baseline procedure or the mucosa has not healed from prior sinus surgery or ESS.
- d. Patient had prior frontal SBD or ESS with corticosteroid containing stents, packing materials or implants (e.g., PROPEL, PROPEL Mini or PROPEL Contour) within approximately 1 year prior to the baseline procedure.
- e. Patient had prior frontal SBD without corticosteroid containing stents, packing materials or implants, or prior balloon dilation in other sinuses with corticosteroid containing stents, packing materials or implants,  $\leq 30$  days prior to the baseline procedure.
- f. Expanded amount of ethmoid sinonal polyps extending beyond the middle meatus (grade  $> 2$ ) unless reduced  $\geq 30$  days prior to the baseline procedure.
- g. Patient has oral-steroid dependent condition such as chronic obstructive pulmonary disease (COPD) or other conditions.

- h. Known history of allergy or intolerance to corticosteroids or mometasone furoate.
- i. Patients with a known hypersensitivity to lactide, glycolide or caprolactone copolymers.
- j. Patients with electronic devices in direct connection to the brain or the nervous system such as implantable neurostimulators (e.g., deep brain stimulation), programmable CSF shunts.
- k. Patients with monopolar pacemakers (older designs, with lower resistance to interference) or ICD's (implantable cardioverter defibrillator).
- l. Patients with implantable, body worn devices such as insulin pumps.
- m. Patient has clinical evidence of acute bacterial sinusitis (e.g., acute increase of purulent discharge, fever).
- n. Patient has clinical evidence or suspicion of invasive fungal sinusitis (e.g., bone erosion on CT scan, necrotic sinus tissue).
- o. Patient has an active viral illness (e.g., COVID-19, flu, shingles).
- p. Patient has active bacterial infection other than in the sinuses requiring oral antibiotics, unless resolved prior to baseline procedure.
- q. Patient has clinical evidence of disease or condition that is likely to compromise survival or ability to complete follow-up assessments through Day 180 (end of study).
- r. Patient has used parenteral or injected steroids (e.g., Kenalog) ≤ 30 days prior to the baseline procedure.
- s. Patient has used oral steroids, budesonide or other sinus steroid irrigations/rinses or drops, nebulized steroids administered nasally ≤ 14 days prior to the baseline procedure.
- t. Patient is currently participating in another clinical trial.

Intraprocedural exclusion criteria:

- u. Patient fails the field mapping check during the pre-baseline procedure navigation assessment.
- v. Other than implantation of one PROPEL Contour on one frontal sinus side of the subject at the baseline procedure, use of corticosteroid-eluting sinus implants (PROPEL, PROPEL Mini, PROPEL Contour, SINUVA®) or other steroid soaked packing materials in any sinuses.

### **11.3 Subject Withdrawal**

Study subject may be withdrawn or terminated for the following reasons:

- Subject death
- Concomitant disease or any pre-existing disease or condition that precludes subject's participation
- Subject voluntarily chooses not to participate further in the study.

- Subject's non-compliance with study procedures
- Lost to follow-up: the subject has missed a study visit and three documented attempts to contact the subject are unsuccessful. A subject who misses a study visit should be contacted by site personnel to determine the reason for the missed visit, which should be documented in the subject's study records. Note: A subject who misses a study visit but attends a subsequent visit will no longer be considered lost to follow-up, and their previous missed visits will become 'missed visits'.
- In the clinical investigator's opinion, a significant safety concern arises that requires subject discontinuation.
- In the clinical investigator's opinion, it is not in the best interest of the subject to continue study participation.
- In the sponsor's or IRB's opinion, it is not in the best interest of subject to continue the study.

If a subject decides to withdraw from the study, clinical investigator should follow patients with ongoing AEs till resolution according to the standard of care. Data collected up to the point of subject withdrawal or termination will be maintained in the study database and included in analyses as appropriate. All enrolled subjects, including those withdrawn or lost to follow-up, will be accounted for and documented.

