### **19.3 Blinding**

The independent reviewer of CT images will be blinded to treatment assignment. Subjects, treating investigators and clinical research coordinators will be unblinded, as they will be attending the placement procedure.

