9.3.4 Sensitivity Analyses

Sensitivity analysis for medical or surgical intervention

Because intervention with oral steroids or surgical intervention may confound the primary efficacy endpoint, the following method will be applied to the analyses in cases where such interventions are performed:

- If a subject initiates oral steroids or undergoes revision ESS for CRS conditions attributable to the FSO/frontal recess before Day 45, this represents treatment failure. If the intervention occurs on the treatment side or both sides, the FSO cross-sectional area of the treatment side will be imputed with the value of the control side (i.e., side-to-side difference in FSO area is

zero). If the intervention occurs on the control side only, the FSO cross-sectional area in the control side will be imputed as zero (i.e., totally occluded).

- If a patient initiates oral steroids for other reasons not involving the FSO/frontal recess before Day 45, this does not represent treatment failure. In this scenario, the side-to-side difference in FSO cross-sectional area for that subject will be imputed as zero.
- No other data imputation rules will be applied in the planned statistical analyses.

Sensitivity analysis for missing data

Subjects with a missed visit, lost to follow-up, or with FSO cross-sectional area ‘unable to view’ by the independent, blinded reviewer will be considered as missing data. If more than 10% of the primary efficacy data are missing, the following imputation analyses will be performed to test the robustness of the primary efficacy conclusion in order:

- *Worst-case imputation.* The worst case of side-to-side difference in FSO area is zero. If the primary efficacy endpoint passes (p -value < 0.05) using worst-case imputation, then there is no need to do a best-case imputation analysis.
- *Best-case imputation.* The best case of side-to-side difference in FSO area is equal to the average for the treatment site.

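### Protocol 11.3 lets an already implanted subject be withdrawn on discretionary grounds with no provision for the Day 45 CT, a loss that the planned missing-data analyses would hardly register if it biased the result

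*Protocol*

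**What the plan says.** Protocol 11.3 gives eight reasons for ending a subject's participation, introduced by the words "Study subject may be withdrawn or terminated for the following reasons". Three of them end data collection by their nature: death, the subject's own choice, and loss to follow-up. The other five depend on someone's judgement. They include "Subject's non-compliance with study procedures", "In the clinical investigator's opinion, it is not in the best interest of the subject to continue study participation" and "In the sponsor's or IRB's opinion, it is not in the best interest of subject to continue the study", together with a disease that precludes participation and a safety concern. Nothing restricts them to subjects not yet randomised.

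On data, 11.3 says: "Data collected up to the point of subject withdrawal or termination will be maintained in the study database and included in analyses as appropriate". It does not mention seeking any assessment afterwards.

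Protocol 19.3 says: "Subjects, treating investigators and clinical research coordinators will be unblinded, as they will be attending the placement procedure". It does not give the sponsor's status.

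SAP 9.3.4 describes missing primary data as "Subjects with a missed visit, lost to follow-up, or with FSO cross-sectional area" that the core lab reader could not see. Withdrawal is not named. If more than 10% of the primary data are missing, a side-to-side difference of zero is imputed as the worst case. A best-case imputation follows only if that analysis does not pass. SAP 6.7 has a rule for early withdrawals, but it assigns treatment failure, which suits a binary endpoint and not a difference in mm².

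**The concern.** Before randomisation the discretionary reasons do no harm, because the subject is simply a screen failure. After implantation they act differently. The study intervention is one placement (Protocol 12.3.4), so there is no continuing study treatment to stop. Removal of the implant is already left to the investigator by Protocol 12.4, whether or not the subject stays in the study. What withdrawal ends is follow-up, including the Day 45 CT that carries the primary endpoint.

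The treating investigator knows which side was implanted and grades both sides by endoscopy at Day 21, before that CT. A discretionary withdrawal between those visits can therefore be made with both assignment and early outcome in view. Each one removes a whole pair from the primary t-test. If withdrawals were more frequent when the implanted side did badly, the estimated difference would be too large.

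**Working it through.** **Inputs.** From SAP 4.4: difference 9 mm², SD of the difference 18 mm², two-sided alpha 0.05, 56 evaluable subjects, up to 20% non-evaluable, 80 randomised. From SAP 9.3.4: trigger above 10% missing, worst-case value zero. The documents do not say how many subjects would be withdrawn or what their differences would be. Those figures below are assumptions, and all 80 are taken to be in the ITT population.

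**1. The plan's own figure.** A one-sample t-test on the side-to-side difference reaches 95.0% power at n = 54 and 95.7% at n = 56. The stated 56 meets the target of at least 95%.

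**2. Effect on the estimate.** Let k subjects with mean difference d be withdrawn, with the remaining 80 - k averaging 9 mm². The full-set mean is [(80 - k) × 9 + k × d] / 80, while the analysed mean stays at 9.0.

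| k | d (mm²) | Full-set mean (mm²) | Analysed minus full-set |
|---|---|---|---|
| 4 | -9 | (684 - 36)/80 = 8.10 | +0.90 (11% too high) |
| 4 | -18 | (684 - 72)/80 = 7.65 | +1.35 (18% too high) |
| 8 | -9 | (648 - 72)/80 = 7.20 | +1.80 (25% too high) |
| 8 | -18 | (648 - 144)/80 = 6.30 | +2.70 (43% too high) |
| 8 | +9 | (648 + 72)/80 = 9.00 | 0 |
| 8 | +27 | (648 + 216)/80 = 10.80 | -1.80 (17% too low) |

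The last two rows show that the bias can vanish or reverse. It depends on whether withdrawal is related to the treatment-minus-control difference.

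**3. The trigger.** 8/80 = 10.0%, which is not more than 10%, so no missing-data imputation is run. 9/80 = 11.25% starts it.

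**4. What zero imputation does.** Let S be the sum of the n observed differences and W their sum of squares. Then t = S / √[(nW - S²)/(n - 1)]. Adding m zeros changes neither S nor W; it only replaces n by n + m. With 64 observed, mean 9 and SD 18:

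- S = 64 × 9 = 576, and W = 63 × 324 + 64 × 81 = 25,596.
- Observed cases: t = 576 / √[(64 × 25,596 - 331,776)/63] = 576/144 = 4.00.
- With 16 zeros added: t = 576 / √[(80 × 25,596 - 331,776)/79] = 576/147.4 = 3.91.

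The mean falls from 9.0 to 7.2, but the SD falls too and n rises, so the test is almost unchanged:

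| Missing of 80 | Observed mean | p, observed cases | p, zeros imputed |
|---|---|---|---|
| 8 | 9 | 0.00007 | 0.00007 |
| 16 | 9 | 0.00017 | 0.0002 |
| 8 | 5 | 0.0212 | 0.0213 |
| 16 | 5 | 0.0299 | 0.0301 |

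The 8-missing rows show what the imputation would do if it were run; under the trigger it would not be.

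**5. How bad the losses must be to matter.** With SD 18 among the missing as well, significance is lost when their mean difference falls to the following values:

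- Observed mean 9 mm²: about -32.5 mm² with 8 missing, about -14 mm² with 16.
- Observed mean 5 mm²: about -5 mm² with 8 missing, about 0 mm² with 16.

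**6. A ceiling.** In 40,000 simulated trials with no true effect, the worst differences among 80 were deleted. Losing the 4 worst raised the chance of a significant result favouring treatment from the nominal 2.5% to 19.0%, and it was still 19.0% after zero imputation. Losing the 8 worst gave 47.8% both ways. Losses this closely tied to outcome are an extreme, not a forecast. The comparison shows that the imputation does not detect them.

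**The case against.** The strongest reply is that the missing-data plan does reach these subjects. A reader might infer that, because SAP 9.3.4 does not name withdrawals, they neither count toward the 10% nor get imputed, and that the loss goes wholly untested. The documents do not support that. The trigger is worded in terms of missing primary data, and a withdrawn subject with no Day 45 CT is naturally a missed visit. SAP 6.7 sends missing data for every efficacy endpoint to 9.1 and 9.3.4, and SAP 7 summarises the reasons for discontinuation. What remains is a small ambiguity, since SAP 6.7 treats missed visits and early withdrawals under separate rules.

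A second tempting inference is that a subject doing badly takes a barred steroid and is then removed as non-compliant. This is largely handled elsewhere. Protocol 14 and 15.1 allow for clinical need. SAP 6.7 sets the continuous endpoint to missing after such use whether or not the subject is withdrawn. The first sensitivity analysis in 9.3.4 imputes cases of oral steroids or revision surgery for frontal disease without any 10% condition, so it is wrong to say that no planned analysis bears on outcome-related events.

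Third, a reader might take the sponsor to be unblinded as well. Protocol 19.3 does not say so, and 11.3 does not say who judges non-compliance.

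Fourth, both sides leave together, and concomitant disease or poor compliance has no evident link to which side does worse. At an observed 9 mm², 8 missing subjects averaging -9 mm² would leave p at about 0.0009. This objection stands against any claim that bias is likely or that the trial's conclusion is at risk at the design effect. It does not answer the simpler point that these CTs need not be lost. Nor does the permissive wording of 11.3: it does not forbid a later CT, but it asks nobody to obtain one.

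**Conclusion.** The point holds as a cheap improvement to Protocol 11.3. Discretionary withdrawal after Day 0 can only remove outcome data, and the treating investigator knows the implanted side. The loss may be related to outcome, but its number and direction are unknown, and the documents give no evidence that it will be. On the assumed scenarios the estimate could be 11% to 43% too high, unaffected, or too low. At an observed 9 mm² the significance of the result is robust to 8 such losses unless they are extreme; at an observed 5 mm² it is much less so.

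The planned missing-data analyses would not reveal such a bias: none runs at 8 of 80 or fewer, and above that zero imputation leaves the t-test almost where it was. Obtaining the scan is therefore worth more than any re-reading of SAP 9.3.4.

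**What to change.** In Protocol 11.3, limit the reasons that end data collection to death, withdrawal of consent and loss to follow-up. For the remaining reasons, state that a randomised subject stays in the study and is still asked to attend the scheduled Day 45 and Day 180 CTs and to have adverse events collected, unless the subject declines or the investigator records a safety reason against the assessment.

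As a clarification only, add subjects withdrawn before Day 45 to the missing-data list in SAP 9.3.4. Alone this changes almost nothing, because 8 of 80 would still not start the analysis and zero imputation has little effect.

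The cost is one protocol paragraph and one SAP phrase. The downside is some extra effort at sites to bring subjects back for visits that are already in the schedule.
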